1. For single-site studies - CMCVAMC is the only institution involved. Yes No
2. For multi-center studies.
 - 2.1. CMCVAMC is the Coordinating Center in which the PI is the lead investigator. Yes No N/A
 - 2.2. Provide the name of the Coordinating Center. Yes No N/A
 - 2.3. List the name of the other sites involved.
 - 2.4. Provide the FWA numbers for each of the other sites involved.

THE FOLLOWING INFORMATION MUST BE CMCVAMC-SPECIFIC, THAT IS, SPECIFIC TO WHAT WILL BE DONE WITH CMCVAMC-RECRUITED VETERANS.

H. Background and Significance: (Describe succinctly and clearly the past findings which justify the plan for this project. A summary of the relevant literature in the area of interest and reports of previous studies should be included.)

Peer support and particularly mentors have been shown to help African American diabetic veterans with poor diabetes control improve their glucose control. Ongoing studies are testing whether mentors can help non-veterans and populations including a larger sample size of women. Peer mentors may be particularly effective in a VA setting where many patients lack social support and a culture of camaraderie is strong. However, it is unknown if improvements persist once mentoring stops, how to best sustain such programs and whether peer support models would be effective in veterans from all ethnic racial groups.

Purpose of the Project: (Clearly provide the purpose of this research project.)

In this study, we propose a randomized controlled trial of poorly controlled diabetic veterans in which poorly controlled veterans of all race/ethnicities first enroll as mentees in a program for diabetic veterans and then as mentors to test a model of sustainability. In addition, given a growing literature that being a mentor is good for your health besides from creating sustainability for the program it may help sustain

effects. This study will have 4 arms: 1. Usual care (enrolled at two different time points); 2. Peer mentoring where mentors are veterans who were once in poor control but are now in good control; 3. Peer mentoring where the mentoring comes from former mentees from arm 2 (mentoring FFM); and 4. Former mentees from arm 2 not randomized to becoming a mentor. Ultimately we aim to create programs that can serve to sustainably support VA Patient Aligned Care Team (PACT) efforts.

Describe the Research Questions or Hypotheses (that is, what questions are you trying to address by conducting the research.)

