Our primary aims are as follows.

1. Test the effectiveness of a peer mentor model in a mixed race population of poorly controlled diabetic veterans.
H1: Compared to usual care, veterans in the peer mentor arms will have improved hemoglobin (HbA_{1c}), blood pressure, LDL levels, DM quality of life, and depression scores regardless of race or ethnicity at the end of the intervention (tested at 6 months) and effects will persist (tested at 12 and 18 months).
2. Test the effectiveness of using former peer mentees as peer mentors.
H2: Compared to usual care, veteran who receive peer mentoring from former mentees will have improved hemoglobin (HbA_{1c}), blood pressure, LDL levels, DM quality of life, and depression scores at the end of the intervention (tested at 6 months) and effects will persist (tested at 12 and 18 months).
3. Assess the effects of becoming a mentor on those who were originally mentees.
H3: Compared to past mentees who are not randomized to becoming a mentor, past mentees randomized to becoming a mentor will have better glucose control, blood pressure, LDL levels, DM quality of life, and depression scores.
4. Conduct a rigorous qualitative evaluation examining in-depth the mentor-mentee relationship, the transition to becoming a mentor, qualities of a successful mentor, and factors relevant to broader program implementation.

Secondary Aims:

5. In those randomized to being a mentee, explore mentor characteristics associated with improved HbA_{1c}. Predictors to be evaluated include past mentoring dose of the current mentor, the mentor's past change in HbA_{1c}, the mentor's starting HbA_{1c}, current mentoring dose provided by the mentor, mentee's evaluation of the mentor, and mentor's depression score at baseline.

- I. **Primary Outcome Variable(s):** (Define the primary outcome variable(s) used to support the study objectives (e.g. if the objective is to show that treatment A is superior to treatment B in the treatment of subjects with essential hypertension, the primary outcome variable is blood pressure measurement.)

The primary outcome variable will be change in glucose control as measured by the HbA_{1c} assessed at baseline, 6 months, 12 months and 18 months.

- J. **Secondary Outcome Variable(s):** (Define the secondary outcome variables. Such measured variables should also include the timing of measurement.)

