2.3. For retrospective research studies, provide the “look-back” period. (e.g., December 1, 1999 through December 31, 2008.)

[figure not shown]
3. Study Duration

3.1. Provide the estimated length of time to enroll all subjects and complete the study.

We want to enroll a total of 492 poorly controlled diabetic veterans and 206 mentors with currently good glucose control. In stage 1 there will be 206 poorly controlled diabetics in the peer mentoring arm and 206 mentors. Mentors who withdraw from the study will be replaced by additional mentors to ensure that all 206 poorly controlled diabetics in the peer-mentoring arm have mentors. In stage two there will be 144 mentors (former mentees) of which 72 will be randomized to being a mentor and 72 will be randomized to usual care. In addition, there will be 128 poor controlled diabetics 56 of whom will be in usual care and 72 of whom will be randomized to receiving peer mentoring from FFM. We project being able to enroll 7-8 new poorly controlled diabetics per week with two research assistants. Even considering the staggered start times, we anticipate it will take 14-16 months to complete enrollment and another 18-24 months to complete follow-up for a total of 38-40 months. After that we anticipate it will take an additional 1-2 months to complete the analysis. See sample size section for further description of required sample.

3.2. Explain the expected duration of subject participation including any follow-up.

The active time for each participant in the study will be roughly 18-24 months depending on which arm they are randomized to. 12-18 months of face-to face visits with an additional 6 months after the last in-person visit where each participant’s electronic medical record (EMR) will be under electronic review. Figure 2 depicts the flow of participants through the study.

Figure 2: Flow of Participants Through Study

3.3. Specify the projected date of completion of the proposed study.

Enrollment started September 27, 2012 and we anticipate completion of the study by December 31, 2015

4. **Drug Information** (If not applicable state, "Not Applicable.") **N/A**

- 4.1. Specify if the drug or biological agent is:
 - 4.1.1. FDA approved
 - 4.1.2. Used for off-label purposes
 - 4.1.3. Not yet FDA approved.
- 4.2. Include the FDA Investigational New Drug (IND) number for all non-FDA approved and off-label drugs, biological agents or nutritional supplements. If not applicable state, "Not Applicable."

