At the end of 6 months, those randomized to receiving a mentor in stage 1 will be re-randomized to either becoming a mentor (arm 2) or not becoming a mentor (arm 4). Those who do not become a mentor will continue to be followed. Those randomized to being a mentor will become mentors for arm 3 participants. For arm 3, matching will be tailored to the best of our ability since the pool of mentors will be limited to those who were previously mentees. We have built in over-enrollment into stage 1 to allow for some loss to follow-up and selective removal of participants who might be inappropriate mentors. Potential mentees for stage 2 will be identified and contacted in the same manner as those identified for stage 1. Those interested in participating will be randomized to usual care or mentoring from FFM. As with stage 1, participants will receive \$50 to reimburse them for their time for all required in person visits.

Procedures: As mentioned there will be 4 arms. Randomization into each arm is described above.

Arm 1 Usual Care: They will complete all planned surveys, interviews and blood draws (baseline, 6 months, 12 months). In addition, all participants' medical health record will be under electronic review for an additional 6 months after their last visit. They will be notified of their starting HbA1c and the American Diabetes Association (ADA) and VA recommended goals for HbA1c. No additional interventions will be provided. All participants will be called at one month and three months to check in and assess for hypoglycemic events (based on our past previous work we anticipate that these events will be rare and not differ by arm).

Arm 2 Peer Mentoring: In addition to being notified of their starting HbA1c and ADA and VA recommendations for HbA1c, arm 2 will be told that within the next 1-3 weeks we will find them a peer mentor who will start calling them. They will be told that they are expected to talk with the mentor at least once a week for 6 months but they can talk as much as they want. We will also

explain that we will not be setting up a face-to-face introduction but that it is fine for the two of them to meet in person if they desire. Finally, participants will be reminded that in six months time they may become a mentor. We will train them to be mentors and provide them with a mentee who is in poor diabetes control.

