In order to assure 72 in each arm for stage 2, we will need a total of 144 mentees in stage 1. Again, to protect against possible attrition, we inflate that by 16% and enroll 171 mentees in stage 1. A corresponding number of mentors (171) will be recruited for stage 1. There will be no randomization of mentors in stage 1. Since usual care for stage 1 can be combined with usual care for stage 2, there is no need for a 1:1 randomization. Initially, a 1:1 randomization was used, but after evaluation we believe we can switch to a 2:1 randomization to avoid recruiting more usual care patients than necessary. With this change we will enroll approximately 139 patients to usual care in stage 1.

The combined number of poorly controlled diabetic patients receiving usual care will be approximately 195. The number of poorly controlled diabetic patients receiving peer mentoring will be 232 (171 in stage 1 and 72 in stage 2). The number of mentors in stage 1 will be 171, and the number of mentors in stage 2 will be 72 (from among those who received mentoring in stage 1). The total number of patients in the study will be 594.

A recent analysis of clinical data from the CMC VAMC and its surrounding CBOCs indicate that in the last year there were 1,248 patients who would have qualified to be mentees and 1,810 who would have qualified to be mentors.

4.2. Define plans for data and statistical analysis, including key elements of the statistical plan, stopping rules and endpoints.

For Stage 1: We will test these primary hypotheses using an unadjusted intent-to-treat analyses, i.e., with adjustment for only baseline HbA_{1c}. The primary tests will assess the significance of the coefficients associated with the treatment assignment in a longitudinal linear model of the repeated HbA_{1c} as a function of treatment, where the active group (peer mentoring) is compared to the control group via an indicator variable. Standard t-tests will determine whether a significant difference in HbA_{1c} improvement occurred between the treatment arm compared to the control arm. To account for the fact that we are doing multiple tests, we will use the Bonferroni method and consider a treatment to be significantly different than the control if the p-value is less than $0.05/2=0.025$.

| Stage 2 Analysis:

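### As written, the H1 comparison at months 12 and 18 does not isolate whether benefit persists after mentoring stops, because 72 stage 1 mentees are randomised into an active mentor role at month 6

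*Combined protocol and SAP*

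**What the plan says.** - **The question.** Section H (Background and Significance) says "it is unknown if improvements persist once mentoring stops". H1, under the primary aims, treats month 6 as the end of the intervention and adds that "effects will persist (tested at 12 and 18 months".
- **Month 6.** Section M.1.1 (Study Procedures) says that the stage 1 mentees "will be re-randomized to either becoming a mentor (arm 2) or not becoming a mentor (arm 4". Section K.3.1 (Study Duration) gives the numbers: "72 will be randomized to being a mentor and 72 will be randomized to usual care". New mentors are trained, contacted monthly and paid for weekly calls (M.1.1, Arm 2).
- **Expected effect of that role.** H3 expects former mentees who become mentors to have better glucose control than those who do not. The Purpose statement says that being a mentor may help to sustain effects.
- **Analysis.** In U.4.2 (For Stage 1), "the active group (peer mentoring) is compared to the control group via an indicator variable". No term represents the month-6 re-randomisation, and no follow-up time is named. Arm 4 enters the analysis plan only in the H3 comparison.
- **Number of stage 1 mentees.** K.3.1 states: "In stage 1 there will be 206 poorly controlled diabetics in the peer mentoring arm". U.4.1 states: "we inflate that by 16% and enroll 171 mentees in stage 1". Both figures are carried through below.

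**The concern.** At months 12 and 18 the stage 1 mentored group contains people whose mentoring ended and people who moved into a second randomised intervention lasting to about month 12. A single indicator estimates the lasting effect of having been mentored plus a share of the effect of being a mentor. Adding visit or treatment-by-visit terms does not separate the two, because both sit under the same indicator.

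If H3 is true, H1 leans towards showing persistence even where there is none. A positive month-12 result could then be reported as lasting benefit from six months of mentoring when a continuing second role produced it. If the mentor role worsened control, real persistence would be masked. The month-6 comparison is unaffected, because re-randomisation takes place at that visit.

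**Working it through.** **Inputs.** Effect 0.8, SD 1.6, 64 per arm raised to 72 (U.4.1); stage 1 alpha 0.05/2 = 0.025 (U.4.2); 72 mentors and 72 non-mentors (K.3.1). Stage 1 usual care is 139 (U.4.1) or, from K.3.1, 492 − 206 − 128 = 158.

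**The plan's own figure.** For 80% power at two-sided 0.05, the two-sample t calculation gives 63.8, so 64 per arm; 64/0.9 = 71.1, so 72. The plan's figure is reproduced.

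**Share who become mentors.** 72/206 = 35% or 72/171 = 42% of those enrolled; 72/144 = 50% of those re-randomised.

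**Artefact at month 12.** Suppose that nothing carries over from being mentored and that the mentor role has effect M. The documents give no value for M. I use 0.8, the effect the plan is sized for, and 0.4. Then:

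- pooled difference = M × 72/n, where n is the number of mentees analysed;
- SE = 1.6 × √(1/n + 1/c), where c is the number in usual care;
- probability of significance = Φ(difference/SE − z) + Φ(−difference/SE − z), with z = 1.96 at 0.05 and 2.24 at 0.025.

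| M | Mentees v usual care | Pooled difference | SE | Significant at 0.05 | Significant at 0.025 |
|---|---|---|---|---|---|
| 0.8 | 206 v 158 | 0.28 | 0.169 | 38% | 28% |
| 0.8 | 171 v 139 | 0.34 | 0.183 | 45% | 35% |
| 0.8 | 144 v 158 | 0.40 | 0.184 | 58% | 47% |
| 0.8 | 144 v 139 | 0.40 | 0.190 | 56% | 45% |
| 0.4 | 206 v 158 | 0.14 | 0.169 | 13% | 8% |
| 0.4 | 171 v 139 | 0.17 | 0.183 | 15% | 9% |

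The rows with 206 and 171 count everyone enrolled, as intent-to-treat requires. The rows with 144 apply only if the analysis is limited to those re-randomised.

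**Arm 4 against stage 1 usual care, unweighted, true difference 0.8.**

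| Arm 4 v usual care | SE | Power at 0.05 | Power at 0.025 |
|---|---|---|---|
| 72 v 158 | 0.228 | 94% | 90% |
| 72 v 139 | 0.232 | 93% | 88% |
| 64 v 142 (10% loss) | 0.241 | 91% | 86% |
| 64 v 125 (10% loss) | 0.246 | 90% | 84% |

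All figures are simple two-group comparisons at one visit, without baseline adjustment.

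**The case against.** **The trial can answer the question.** A reader might infer that the trial cannot say whether benefit outlasts mentoring. The documents do not support that. Arm 4 is randomised, takes no mentor role and is followed in the same way as arm 2, with an in-person 18-month visit. H2 also tests persistence at 12 and 18 months in arm 3, for whom no later mentor role is described. This objection stands, so the gap is in the analysis plan. H2 does not fill it, because it concerns mentoring by former mentees, a different intervention.

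**The pooled contrast is legitimate.** The Purpose statement describes veterans enrolling first as mentees and then as mentors, and arm 2 patients are told at entry that they may become mentors. Comparing everyone as randomised at stage 1 estimates the effect of that programme. This stands too. The contrast is worth reporting, but it does not answer what H1 and the background ask.

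**Pooling after month 6 is not stated outright.** The stage 1 paragraph does not say how the re-randomised groups enter later visits, and the documents number them as arms 2 and 4. One might equally infer that only the new mentors count as peer-mentored at month 12. Neither reading is established. The accurate charge is that the one model given does not separate the groups.

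**Half is too high a share.** It is right for those re-randomised; among all enrolled it is 35-42%.

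**H3 would expose the problem.** A mentor-role effect of 0.8 is what H3 is sized to detect, so a careful reader could see it. That reduces the risk of a wrong conclusion but does not supply the missing contrast.

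**Month 18 needs more.** The role ends near month 12, so an artefact at month 18 also requires the mentor-role effect to outlast the role while the mentoring effect does not last.

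**Conclusion.** The concern holds as a gap in the analysis plan. The H1 contrast at months 12 and 18 mixes persistence of mentoring with the effect of a second randomised role, and no contrast of arm 4 with usual care is specified.

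If mentoring leaves no lasting effect and the mentor role is worth 0.8, intent-to-treat analysis at month 12 would show about 0.28 to 0.34 and declare persistence 38-45% of the time at 0.05, or 28-35% at 0.025. If only the 144 re-randomised were analysed, the difference would be 0.40 and the figures 56-58% and 45-47%. With a mentor-role effect of 0.4 and all mentees counted, they fall to 13-15% and 8-9%. These sizes rest on the assumed mentor-role effects, the plan's SD of 1.6 and zero carry-over. No size is claimed for month 18. The month-6 comparison, H2 and H3 are not affected.

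**What to change.** 1. Keep the full stage 1 comparison at month 6.
2. Prespecify arm 4 versus stage 1 usual care at month 12 as the H1 test of persistence after mentoring stops, with month 18 as a supporting analysis.
3. Give arm 4 patients weight 2, mentees never re-randomised weight 1, and those randomised to become mentors weight 0. The weights then sum to the number enrolled: 2 × 72 + 62 = 206, or 2 × 72 + 27 = 171. This matters because M.1.1 allows loss to follow-up and selective removal before re-randomisation, so arm 4 alone is a selected subset.
4. Weights cannot supply missing outcomes. Handle those lost or removed before re-randomisation with the longitudinal model and a sensitivity analysis.
5. At month 18, use EMR values in both groups. Usual care has no in-person visit then, while arm 4 does. The planned chart abstraction covers readings from study entry onwards, so it can supply both.
6. Report the pooled contrast separately, labelled as the effect of the whole mentee-then-mentor programme.

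**Cost.** SAP wording and one weighted contrast, with no new patients or visits. The loss is precision: the unweighted SE is about 0.23 instead of about 0.17-0.19. Power for 0.8 stays at about 93-94% at 0.05 and 88-90% at 0.025, or 90-91% and 84-86% after 10% loss.

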2.1. Provide

- 2.1.1. the mode of data collection, e.g. telephone, in-person, questionnaire, interviews,

Data will be collected mostly by in-person survey, interview and lab tests. In addition, mentors will receive short reinforcement calls each month at which time we will collect data about how many times the mentor talked to the mentee in the month. Hypoglycemic symptoms will be assessed by phone at 1 and 3 months (additionally at 7 and 9 months for arms 2 and 4) . Electronic medical records will be reviewed 6 months after the last in person visit. See Table 1 and 2 for details.

- 2.1.2. the precise plan for how data is to be collected or acquired

Surveys will be read to participants and answers will either be directly input into a computer database or written onto paper forms and then transferred to a data base at a later time. The data base will reside on VA servers behind the VA firewall and will never be removed from the server. Paper records will be stored at CHERP behind an electronically locked entrance, a key-locked door and in a key-locked cabinet.

Qualitative interviews will also be read to participants and answers will be voice recorded. Interview data will be stored on the VA server and will be behind VA firewalls This data will be temporarily shared with Alpha Transcription, and University of Pennsylvania's Mixed Methods Research Lab, transcribing and coding respectively. Both companies are approved vendors with appropriate VA approved data security in place.

Data about the number of calls per month made by the mentor will be collected over the phone, and again responses will either be entered directly into a database or first onto paper and then into the database.

Data about hypoglycemic symptoms will be collected over the phone and responses will either be entered directly into a database or first onto paper and then onto the database.

Lab results will be obtained from the lab or via CPRS and entered into the secure research database.

Charts will be abstracted for additional HbA1c, LDL, and blood pressure readings 6 months after the last face-to-face visit.

- 2.1.3. exact location where data will be collected,

CMC VAMC and the CMCVAMC Annex (for in person, phone and chart derived data).

2.1.4. exact location where data entry will take place.

All data entry will occur either at the CMC VAMC or the CMC VAMC Annex. Paper files for the study will be housed at the CMC VAMC annex in locked filing cabinets. Data will be stored on VA servers behind the VA fire wall. .

2.1.5. the "title" of individual(s) collecting the data and analyzing the data, e.g. principal investigator, research coordinator.

A Project manager and/or research coordinators will be collecting data and entering it into the database. The Principal investigator and a master's level programmer will be analyzing the data. Identifiable data will not be removed from CMC VAMC servers. Access to identifiable data will be limited to those who require access including the project manager and research coordinators, principal investigator, and the programmer.

2.2. Provide a time line for each aspect of the study.

Baseline: Obtain consent, complete baseline survey, randomize, obtain blood.

For arm 2 (and 4) also: Identify mentor, obtain consent from mentor, complete mentor baseline survey, train mentor, obtain blood from mentor, have mentor start calling mentee.

6 months: Complete follow up survey, interviews, and blood for mentors and mentees.

For arm 2 also: Train arm 2 participants to be mentors and match them to mentees (participants in arm 3).

12 months: Complete follow up survey, interviews, and obtain blood from arms 1, 2, 3, and 4.

18 months: Complete follow up survey, interviews, and obtain blood from arms 2, and 4.

18 months-24 months: Monitor electronic health record for arm 1, 2, 3, and 4.

Ongoing: Call all mentors every month to reinforce training and determine mentor-mentee call frequency. Call all mentees at 1 and 3 months to assess hypoglycemic symptoms.

